6.14.8.2. Definitions of Immunogenicity Assessment Periods

Immunogenicity Baseline Observations: Screening period for immunogenicity assessment for each patient includes all observations on or prior to first administration of study drug. In instances where multiple baseline observations are collected, to determine patient ADA status the last non-missing immunogenicity assessment prior to first administration of study drug is used to determine treatment-emergent status (see below). In this context, 'missing' includes explicit 'ADA Missing' results, as defined in [Table 7](#).

Immunogenicity Postbaseline Period Observations: Postbaseline period observations for each patient includes all observations after the first administration of study drug.

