6.14. Safety Analyses

All safety evaluations will be based upon the Safety Population as defined in Section 6.2.

Any statistical comparisons for safety data will be performed only between the “All LY3074828” treatment group and Placebo. No pairwise comparisons between LY3074828 induction treatment arms will be performed. Pairwise comparison of LY3074828 maintenance treatment arms will be performed (no comparison to placebo). No multiplicity control procedure will be performed for these tests of safety data.

Safety and tolerability will be evaluated in terms of treatment-emergent AEs (TEAEs), AEs leading to permanent discontinuations of study drug, SAEs, deaths, changes in clinical laboratory test results, and vital signs. These measures will be analyzed for each dose group and combined LY3074828 groups, separately for each study part, as well as across study parts for key summaries.

For all quantitative safety analyses, baseline is defined as the last non-missing assessment recorded on or prior to the date of first study drug injection at Week 0 (Visit 2). However, placebo patients who enter the Extension Period will have their baseline reset. Their new baseline will be defined as the last non-missing assessment on or prior to the date of first injection of study treatment at Week EW0 (Extension Visit 1).

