6.14.1. Extent of Exposure

6.14.1.1. Duration of Exposure

Duration of exposure to study treatment (defined as time since first injection of study treatment in days) will be summarized by treatment group during the Induction Period, the Maintenance Period, the Extension Period.

Duration of exposure during the Induction Period for the Safety Population will be calculated as:

(Disposition date (for those who have discontinued the Induction Period), OR Maintenance/Extension Start date -1 (for those who have completed the Induction Period), OR Date of last study visit in the Induction Period (for those who are still being treated in the Induction Period) – Date of first injection of study treatment + 1)

Duration of exposure during the Maintenance Period will be calculated as:

(Disposition date (for those who have discontinued the Maintenance Period), OR Date of last study visit in the Maintenance Period (for those who are still being treated in the Maintenance Period) – Date of the Visit 8 injection of study treatment + 1)

Duration of exposure to LY3074828 during the Extension Period will be calculated as:

(Disposition date (for those who have discontinued the Extension Period), OR Date of last study visit in the Extension Period (for those who are still being treated in the Extension Period) – Date of the Extension Visit 1 injection of study treatment + 1)

Duration of exposure to LY3074828 for the combined Induction Period and Maintenance Period will be calculated as:

(Disposition date (for those who have discontinued the Maintenance Period), OR Date of last study visit in the Maintenance Period (for those who are still being treated in the Maintenance Period)– Date of first injection of LY3074828 + 1)

Duration of exposure to LY3074828 for the combined Induction Period and Extension Period will be calculated as:

(Disposition date (for those who have discontinued the Extension Period), OR Date of last study visit in the Extension Period (for those who are still being treated in the Extension Period)– Date of first injection of LY3074828 + 1)

The date of first injection of LY3074828 is defined in Table 4.

Table 4 First Injection of LY3074828 by Treatment Group

	Visit of first LY3074828
All patients randomized to LY3074828 (regardless of Week 12 response status)	Week 0 (Visit 2)
Week 12 Inadequate Responders originally randomized to placebo and assigned to LY3074828 at Extension Visit 1	Extension Week 0 (Visit EV1)

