For Time Period A only, the number and percentage of each PT that is not in any of the 3 SMQs will be summarized overall and by individual PT. Only PTs that occur in at least 3 patients receiving LY3074828 will be displayed in this portion of the table.

The PT and LLT are listed for summary in decreasing order of incidence for LY-treated patients. Note that an individual patient may contribute multiple events. Also, a single event may satisfy multiple SMQ, in which case the event contributes to every applicable SMQ.

The analyses of this section will be performed for Induction Period, for Induction and Maintenance Periods combined, and for Induction and Extension Periods combined.

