6.14.8.4. Analyses to be performed

A listing will be provided of all immuno assessments for those patients who at any time had ADA Present. This includes the laboratory ADA assay result (Detected or Not Detected), LY concentration from a simultaneous PK sample, and the clinical interpretation result that combines these (ADA Present, ADA Not Present, ADA Inconclusive, Missing). When Detected, a titer will be included, and TE ADA+ observations will be flagged. Also included, when the NAb assay was performed, will be the laboratory NAb assay result (Detected or Not Detected)

and the NAb clinical interpretation result (NAb Present, NAb Not Present, NAb Inconclusive, Missing).

In the remainder of this section, "ADA result" will refer to the clinical interpretation result, and similarly for NAb.

The number and proportion of patients who are TE ADA+ will be tabulated by treatment group, where proportions are relative to the number of patients who are TE ADA evaluable, as defined above. The tabulation will include all post-baseline observations and will include the number and proportion of patients with ADA Present at baseline, and also the number and proportion of TE ADA+ patients exhibiting NAb+. This summary will be provided for Induction Period, for Induction and Maintenance Periods combined, and for Induction and Extension Periods combined.

For each TE ADA+ patient, a plot will be constructed of titer values from individual samples over time. Samples that are ADA Not Present or ADA Inconclusive will also be indicated.

A summary will be provided of the number and percentage of LY-treated patients experiencing specific TEAE (see [Table 8](#)) by patient TE ADA status (TE ADA+, TE ADA-, TE ADA Inconclusive). The PT will be ordered by decreasing incidence in TE ADA+ status group. For event terms not occurring in any TE ADA+ or TE ADA Inconclusive patient, a summary will be provided of the number of distinct terms reported, but individual PT will not be summarized. This summary will be provided for Induction and Maintenance Periods combined and for Induction and Extension Periods combined.

A listing will be provided of all TEAE alongside ADA data, for any patient who had ADA Present at any time (including baseline) or had any specific TEAE (see [Table 8](#)). This listing includes a time course of ADA (clinical interpretation result plus flags for samples meeting TE ADA+ criteria and for NAb+ samples) along with the TEAE.

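### The antibody baseline rule does not say whether it is reset for placebo patients who start LY3074828 in the extension, so placebo-phase results can enter an LY3074828 summary

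*SAP*

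**What the plan says.** **Immunogenicity rule.** SAP 6.14.8.2 states that "the last non-missing immunogenicity assessment prior to first administration of study drug is used to determine treatment-emergent status", and that "Postbaseline period observations for each patient includes all observations after the first administration of study drug". It contains no exception for placebo patients who later receive LY3074828.

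**General safety rule.** SAP 6.14 ties the baseline for quantitative safety analyses to the first study drug at Week 0, then adds: "However, placebo patients who enter the Extension Period will have their baseline reset". The new baseline is the last assessment on or before the Extension Visit 1 dose. SAP 6.1 has the same reset for efficacy and health outcomes.

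**First LY3074828 dose.** Table 4 in SAP 6.14.1.1 gives Extension Week 0 as the first LY3074828 visit for "Week 12 Inadequate Responders originally randomized to placebo and assigned to LY3074828 at Extension Visit 1". These patients are called switchers below.

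**Where the ADA rule is used.** SAP 6.14.8.4 plans a summary of the Table 8 events (hypersensitivity-type, infusion and injection-site terms) by treatment-emergent (TE) ADA status among patients treated with LY3074828. On periods it says: "This summary will be provided for Induction and Maintenance Periods combined and for Induction and Extension Periods combined".

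**Adverse-event baseline.** SAP 6.14.2 uses the screening period as the baseline for treatment-emergent adverse events (TEAEs), with no reset. For hypersensitivity, SAP 6.14.2.2 says: "The analyses of this section will be performed for Induction Period, for Induction and Maintenance Periods combined, and for Induction and Extension Periods combined". SAP 6.14.2.3 applies the same periods to injection-site reactions.

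**The concern.** A switcher spends the induction period on placebo and is first exposed to LY3074828 at Extension Visit 1. A treatment-emergent antibody finding for LY3074828 should therefore be judged against the state just before that dose. Under 6.14.8.2 as worded, it is judged against Week 0.

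Two programmers could reasonably differ. One would apply the reset from the parent section; the other would apply the specific definition in the subsection. The second reading puts placebo-phase antibodies and events into a summary meant to relate antibodies to events on LY3074828, which serves an exploratory objective (Protocol 6.3).

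A related but separate gap concerns the combined-period hypersensitivity and injection-site tables. There the TEAE baseline is not reset, and the SAP does not say which column holds switchers.

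**Working it through.** The plan states no figure to reproduce. The check compares the rules, counts scheduled samples and illustrates the scale.

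**1. Meaning of first study drug.** Section 6.14 places the first study drug at Week 0 for all patients, and 6.14.1.1 names LY3074828 when it means active drug. For a placebo patient, the 6.14.8.2 baseline therefore precedes the Week 0 placebo infusion.

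**2. Literal consequence.** Suppose a switcher is ADA Not Present at Week 0, Present at a titre of 2 × MRD (minimum required dilution) at Week 4 on placebo, and never higher on LY3074828. Criterion (a) in 6.14.8.3 makes the patient TE ADA+. The patient is also LY3074828-treated, so belongs in the 6.14.8.4 summary. A Table 8 event at Week 6, on placebo, falls within the combined period and is counted there.

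**3. Lost data.** 6.14.8.3 requires a non-missing baseline result. A switcher without a Week 0 result is not evaluable under the literal rule. Protocol Attachment 2 schedules an immunogenicity sample at Extension Visit 1, drawn pre-dose on dosing days, so a valid result before LY3074828 would normally exist.

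**4. Inconclusive rule.** A patient who is not TE ADA+ is TE ADA Inconclusive if at least 20% of post-baseline pre-dose samples are Inconclusive (6.14.8.3). Table 7 assumes that samples on placebo are free of drug interference, so they only enlarge the denominator. Scheduled samples are from Protocol Attachments 1 and 2.

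| Window | No reset | Reset at Extension Visit 1 |
|---|---|---|
| Through extension induction | V3, V4, V6, V7, EV1, EV2, EV3, EV6 = 8; 0.20 × 8 = 1.6, so 2 needed | EV2, EV3, EV6 = 3; 0.20 × 3 = 0.6, so 1 needed |
| Through Extension Week 92 | 8 + 10 = 18; 0.20 × 18 = 3.6, so 4 needed | 3 + 10 = 13; 0.20 × 13 = 2.6, so 3 needed |

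Through extension induction, a switcher with one Inconclusive sample is TE ADA- without the reset (1/8 = 12.5%) and Inconclusive with it (1/3 = 33.3%). This assumes that every scheduled sample counts as pre-dose. If only dosing-day samples count, the sets are V4, V6, EV1, EV3 (4) and EV3 (1). One sample then suffices either way, and the dilution disappears in that window.

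**5. Scale, under assumptions.** The documents give 60 patients per arm, hence 180 on LY3074828. They give no Week 12 response rates, extension entry rate or placebo ADA rate.

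- Switchers = 60 × (1 − placebo response). With response of 20-35% and all non-responders entering: 60 × 0.65 = 39 to 60 × 0.80 = 48.
- Share of the extension cohort, with LY3074828 response of 40-60%: 39/(39 + 108) = 27% to 48/(48 + 72) = 40%.
- Expected switchers turning TE ADA+ on placebo at 1-5%: 39 × 0.01 = 0.4 to 48 × 0.05 = 2.4.
- Wider range, with placebo response of 20-40% and 60-100% entry: about 22 to 48 switchers. The chance of at least one such patient, 1 − (1 − q)^n, is 20-38% at q = 1% and 68-91% at q = 5%.
- Switchers with a Table 8 event on placebo, at an assumed 5-10%: 39 × 0.05 = 2.0 to 48 × 0.10 = 4.8.

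**The case against.** **The reset already exists.** Section 6.14 is the parent of 6.14.8, and a titre ratio is arguably quantitative. The laboratory subsection (6.14.4) and the vital-signs subsection (6.14.5) also restate a baseline without repeating the reset, so silence in 6.14.8.2 does not prove an intended override. This stands in part: the SAP has a reset, and the fault is that its reach is unresolved. It does not remove the fault, because TE ADA status is a classification with its own baseline and post-baseline definitions.

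**Attribution to LY3074828 is mostly not stated.** A reader might infer that all the Induction-plus-Extension tables credit placebo-phase findings to LY3074828. The documents do not support that. Table 1 defines no groups for combined periods, and the general rule in 6.1 is analysis by assigned treatment, which could leave switchers under placebo. Only the summary restricted to LY3074828-treated patients makes the attribution explicit.

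**Hypersensitivity does not depend on the ADA baseline.** This is correct. Resetting the ADA baseline would change no count in 6.14.2.2 or 6.14.2.3. That gap comes from the TEAE baseline in 6.14.2 and the pooling of periods.

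**Impact is small and visible.** The extension is unblinded and has no concurrent placebo. The listings and titre plots in 6.14.8.4 show timing. This stands, but they do not correct the summary counts.

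**Conclusion.** The point holds as an unresolved conflict between SAP 6.14 and 6.14.8.2. If 6.14.8.2 is followed literally, it gives a wrong result in one identified table, the Induction-plus-Extension summary of Table 8 events by TE ADA status. It can also discard evaluable switchers and, if all scheduled samples count as pre-dose, make an Inconclusive classification harder to reach. The undefined switcher column and unreset TEAE baseline in the hypersensitivity and injection-site tables are a separate gap.

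The likely size is about 0 to 2 patients wrongly TE ADA+. That rests on an assumed 1-5% placebo rate and on full entry into the extension, which is optional and so an upper bound. The primary endpoint and the Induction-only tables are untouched.

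A reader might also infer a miscalculated rate, because LY3074828 exposure starts at Extension Visit 1 for switchers while the event window starts earlier. The documents do not support this. The affected tables report numbers and percentages of patients, and exposure-adjusted rates are planned only for Induction and Maintenance (6.14.2.1, 6.14.3).

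**What to change.** 1. In SAP 6.14.8.2, state that for placebo patients entering the extension the immunogenicity baseline is the last non-missing ADA result before the first LY3074828 dose at Extension Visit 1, and that post-baseline begins after that dose.
2. In the Induction-plus-Extension LY3074828 tables of 6.14.2.2, 6.14.2.3 and 6.14.8.4, count switchers' samples and TEAEs only from the Table 4 date of first LY3074828.
3. Reset the TEAE baseline for switchers at the same point.
4. Show switchers in a named column, with their induction data under placebo only.
5. State whether samples from non-dosing visits count as pre-dose in the 20% Inconclusive rule.

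The cost is SAP wording and derived baseline flags for ADA and TEAEs. The pre-dose Extension Visit 1 sample is already scheduled.

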6.14.8.3. Definitions of Patient ADA Status

Patient evaluable for treatment-emergent ADA: A patient is evaluable for treatment-emergent ADA if the patient has a non-missing baseline ADA result, and at least one non-missing post-baseline ADA result.

Treatment-emergent ADA positive (TE ADA+) patient: A patient who is evaluable for treatment-emergent ADA is treatment-emergent ADA positive (TE ADA+) if either of the following holds:

- a. The patient has baseline status of ADA Not Present and at least one post-baseline status of ADA Present with titer $\geq 2 \times \text{MRD}$, where the MRD is the minimum required dilution of the ADA assay.
- b. The patient has baseline and post-baseline status of ADA Present, with the post-baseline titer being 2 dilutions (4-fold) greater than the baseline titer. That is, the patient has baseline status of ADA Present, with titer 1:B, and at least one post-baseline status of ADA Present, with titer 1:P, with $P/B \geq 4$.

Treatment-emergent ADA Inconclusive patient: A patient who is evaluable for TE ADA is TE ADA Inconclusive if $\geq 20\%$ of the patient's post-baseline samples, drawn pre-dose, are ADA Inconclusive and the patient is not otherwise TE ADA+ (i.e. over all postbaseline visits, the patient does not have a TE ADA+ titer).

Treatment-emergent ADA negative (TE ADA-) patient: A patient who is evaluable for TE ADA is treatment-emergent ADA negative (TE ADA-) when the patient is not TE ADA+ and the patient is not TE-ADA Inconclusive.

6.14.8.4. Analyses to be performed

A listing will be provided of all immuno assessments for those patients who at any time had ADA Present. This includes the laboratory ADA assay result (Detected or Not Detected), LY concentration from a simultaneous PK sample, and the clinical interpretation result that combines these (ADA Present, ADA Not Present, ADA Inconclusive, Missing). When Detected, a titer will be included, and TE ADA+ observations will be flagged. Also included, when the NAb assay was performed, will be the laboratory NAb assay result (Detected or Not Detected)

and the NAb clinical interpretation result (NAb Present, NAb Not Present, NAb Inconclusive, Missing).

In the remainder of this section, "ADA result" will refer to the clinical interpretation result, and similarly for NAb.

The number and proportion of patients who are TE ADA+ will be tabulated by treatment group, where proportions are relative to the number of patients who are TE ADA evaluable, as defined above. The tabulation will include all post-baseline observations and will include the number and proportion of patients with ADA Present at baseline, and also the number and proportion of TE ADA+ patients exhibiting NAb+. This summary will be provided for Induction Period, for Induction and Maintenance Periods combined, and for Induction and Extension Periods combined.

For each TE ADA+ patient, a plot will be constructed of titer values from individual samples over time. Samples that are ADA Not Present or ADA Inconclusive will also be indicated.

A summary will be provided of the number and percentage of LY-treated patients experiencing specific TEAE (see [Table 8](#)) by patient TE ADA status (TE ADA+, TE ADA-, TE ADA Inconclusive). The PT will be ordered by decreasing incidence in TE ADA+ status group. For event terms not occurring in any TE ADA+ or TE ADA Inconclusive patient, a summary will be provided of the number of distinct terms reported, but individual PT will not be summarized. This summary will be provided for Induction and Maintenance Periods combined and for Induction and Extension Periods combined.

A listing will be provided of all TEAE alongside ADA data, for any patient who had ADA Present at any time (including baseline) or had any specific TEAE (see [Table 8](#)). This listing includes a time course of ADA (clinical interpretation result plus flags for samples meeting TE ADA+ criteria and for NAb+ samples) along with the TEAE.

Table 8 AE for Analysis with ADA / NAb Results

Events satisfying Anaphylaxis SMQ (narrow or broad)
Events satisfying Hypersensitivity SMQ (narrow or broad)
Events satisfying Angioedema SMQ (narrow or broad)
Events mapping to Preferred Term (PT) of Infusion related reaction
Events mapping to High Level Term (HLT) of Injection site reaction
Events mapping to High Level Term (HLT) of Infusion site reaction
Events mapping to High Level Term (HLT) of Administration site reaction

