Attachment 1. Protocol I6T-MC-AMAC Study Schedule

Study Schedule, Protocol I6T-MC-AMAC
Screening, Baseline, and Induction Dosing Period (1 of 4)

	Induction Dosing Period						
	Screening	Baseline					
Visit No. (V)	V1	V2	V3	V4	V5	V6	V7
Study Week (W)		W0	W2	W4	W6	W8	W11-W12 ^a ET
Day (D)	≤28 from V2	D1	D15 ± 2d	D29 ± 2d	D43 ± 2d	D57 ± 2d	D78-85
Informed consent	X						
Physical examination ^b and weight	X	X					X
Complete medical/surgical history and habits ^c	X						
Demographics	X						
Height ^c	X						
Chest radiography	X ^d						
Randomization (Section 9.3)		X					
Concomitant medications	X	X	X	X	X	X	X
Vital signs (BP and heart rate) ^e Body temperature only at V1 and V2, unless clinically indicated	X	X	X	X		X	X
AEs	X	X	X	X	X	X	X
Dosing ^f		X		X		X	
Partial Mayo score (all subjects)	X	X	X	X		X	
Endoscopy ^g (baseline: only subjects who meet the partial Mayo score and I/E criteria will undergo endoscopy)	X						X
Colon biopsy sample collection (occurs at time of endoscopy)	X						X
Full Mayo score (only patients who meet eligibility criteria for endoscopy will have a full Mayo score)		X					X
Subject diary instruction	X						
Subject diary data review & collection		X	X	X	X	X	X
IBDQ		X		X		X	X

Study Schedule, Protocol I6T-MC-AMAC

Screening, Baseline, and Induction Dosing Period (2 of 4)

	Induction Dosing Period						
	Screening	Baseline					
Visit No (V)	V1	V2	V3	V4	V5	V6	V7
Study Week (W)		W0	W2	W4	W6	W8	W11-W12 ^a /ET
Day (D)	≤28 from V2	D1	D15 ± 2d	D29 ± 2d	D43 ± 2d	D57 ± 2d	D78-85
SF-36		X		X		X	X
PGI-S		X					X
PGI-I				X		X	X
PPD/T-SPOT [®] /QuantiFERON [®] -TB Gold ^h	X						
Read PPD (48-72 hrs after PPD is administered)	X						
ECG ⁱ	X	X					X
HIV, HBV and HCV testing	X						
HBV PCR (only if HBcAb+ with negative HBV PCR test at screening)	X						X
Serum pregnancy test ^j	X						
Urine pregnancy test ^j		X		X		X	X
FSH ^k	X						
Serum chemistry	X	X	X	X		X	X
Hematology	X	X	X	X		X	X
LY3074828 PK samples		X ^l	X	X ^l	X	X ^l	X
Urinalysis	X	X		X			X
NGAL and MMP-9 ^m		X		X		X	X
CRP		X	X	X		X	X
Samples for exploratory biomarkers (whole blood, serum, plasma)		X		X			X
Pharmacogenetics storage sample (DNA)		X					
Immunogenicity samples ⁿ		X	X	X		X	X
Fecal sample (collection instructions in laboratory manual) for Clostridium difficile and biomarker testing	X			X		X	X

Study Schedule, Protocol I6T-MC-AMAC
Maintenance Dosing Period (3 of 4)

	Maintenance Dosing Period												
Visit No (V)	V8	V9	V10	V11	V12	V13	V14	V15	V16	V17	V18	V19	V20

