6.14.2.1. Common Adverse Events

The percentages of patients with TEAEs will be summarized by treatment using MedDRA Preferred Term nested within System Organ Class for the common TEAEs (occurred in $\geq 10\%$ before rounding of treated patients). Events will be ordered by decreasing frequency within System Organ Class.

The percentages of patients with TEAEs by maximum severity will be summarized by treatment using MedDRA Preferred Term nested within System Organ Class for TEAEs. For each subject and TEAE, the maximum severity for the MedDRA level being displayed (Preferred Term, High Level Term, or System Organ Class) is the maximum post-baseline severity observed from all associated LLTs mapping to that MedDRA level. These summary tables will additionally be provided for the Induction, Maintenance and Extension Periods.

In the event differential dropout rates are seen or to further investigate events of interest, summary tables comparing exposure-adjusted incidence rate (that is, person-time-adjusted incidence rates) over the entire time period will be generated for the Induction and Maintenance Periods.

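### The table of events by antibody status uses crude percentages over unequal follow-up, so it can link ADA-positive status with events when no relation exists

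*SAP*

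**What the plan says.** Four parts of the SAP define the table.

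- **What is counted** (6.14.8.4): "number and percentage of LY-treated patients experiencing specific TEAE", by patient status (TE ADA+, TE ADA-, TE ADA Inconclusive). Table 8 lists the events: the anaphylaxis, hypersensitivity and angioedema queries, infusion-related reaction, and injection, infusion and administration site reactions.
- **Who is positive** (6.14.8.3): one qualifying sample is enough. The first route reads "The patient has baseline status of ADA Not Present and at least one post-baseline status of ADA Present", subject to a titer threshold. The second is a fourfold titer rise from a positive baseline.
- **Over what window** (6.14.8.2): "Postbaseline period observations for each patient includes all observations after the first administration of study drug". There is no common cut-off.
- **For which periods** (6.14.8.4): "This summary will be provided for Induction and Maintenance Periods combined and for Induction and Extension Periods combined".

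The neighbouring analyses are planned for Induction alone as well as for the combined periods: TE ADA incidence (6.14.8.4), hypersensitivity (6.14.2.2) and injection site reactions (6.14.2.3). Only the table that joins ADA status to these events lacks an Induction version.

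6.14.8.4 also plans a patient listing of TEAEs beside the ADA time course. Section 6.14.2.1 allows "summary tables comparing exposure-adjusted incidence rate (that is, person-time-adjusted incidence rates) over the entire time period", but only under stated conditions, and it does not say by ADA status.

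**The concern.** Both sides of the table accumulate with time. A patient followed longer gives more samples, any one of which can make the patient positive, and has more time for an event. When patients with short and long follow-up share one crude table, the ADA+ column is enriched with long-followed patients. It can then show a higher event percentage with no relation between antibodies and events.

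An event that precedes the first positive sample also counts in the ADA+ column. That reverses the order of cause and effect for that event, and it can blur a real relation as easily as suggest a false one.

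The table serves the exploratory objective on the effect of anti-LY3074828 antibodies on safety (Protocol 6.3), and it is the only planned summary table relating the two.

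**Working it through.** The documents give no figure for this table, so there is none to reproduce. The check counts samples and then asks what ratio appears when ADA and events are independent.

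**Sample counts, from the immunogenicity rows of Protocol Attachments 1 and 2**

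- Induction, after baseline: V3, V4, V6, V7 = 4.
- Maintenance to Week 104: V9, V11, V13, V15, V17, V19 (6) and V21, V23, V25, V27, V29, V31 (6) = 12. Total 4 + 12 = 16.
- Extension, for a patient given LY in induction: EV1, EV2, EV3, EV6 = 4, so 4 + 4 = 8 on leaving at Extension Week 12 (about 24 weeks). To Extension Week 92, add EV8, EV10, EV12, EV14, EV16 (5) and EV18, EV20, EV22, EV24, EV27 (5), so 8 + 10 = 18 (about 104 weeks).

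**Assumptions (not in the documents)**

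Half of the patients have long follow-up; by Week 12, 8% are ADA+ and 5% have had an event; no dropout. After Week 12 both hazards are multiplied by f. A patient followed to Week 104 then has T = 12 + 92f equivalent weeks, and the cumulative probability is 1 - (1 - p12)^(T/12).

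**Induction+Maintenance, if patients who left at Week 12 are included.** For f = 1, T = 104:

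- ADA+ by Week 104: 1 - 0.92^(104/12) = 0.5145. Event: 1 - 0.95^(104/12) = 0.3589.
- Event share in ADA+: (0.5×0.08×0.05 + 0.5×0.5145×0.3589) / (0.5×0.08 + 0.5×0.5145) = 0.0943/0.2973 = 31.7%.
- Event share in ADA-: (0.5×0.92×0.05 + 0.5×0.4855×0.3589) / (0.5×0.92 + 0.5×0.4855) = 0.1101/0.7027 = 15.7%.
- Ratio 2.03.

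The Induction+Extension columns use the same formula, with the short group at T = 12 + 12f:

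| f | I+M: ADA+ v ADA- | Ratio | I+E: ADA+ v ADA- | Ratio |
|---|---|---|---|---|
| 1 | 31.7% v 15.7% | 2.03 | 29.9% v 19.3% | 1.55 |
| 0.25 | 11.5% v 9.1% | 1.26 | 11.5% v 9.8% | 1.17 |
| 0.1 | 7.3% v 6.8% | 1.08 | 7.4% v 7.0% | 1.06 |

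**Wider ranges for Induction+Maintenance with Week 12 leavers included**

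- Simulation with 20% maintenance dropout, 30-65% entering maintenance, and by Week 12 3-15% ADA+ and 3-8% with an event: 1.5 to 3.1 at constant hazards; 1.07 to 1.31 when both hazards fall to a quarter or a tenth.
- Constant hazards imply high cumulative ADA rates. Before dropout, 1 - 0.97^(104/12) = 23% and 1 - 0.85^(104/12) = 76%; with dropout, about 20-70% of entrants.
- If conversion is instead constant per sample, exposure to conversion rises fourfold (16/4) rather than 8.7-fold (104/12). The range is then 1.35 to 2.18 (30-60% entering, 3-20% ADA+, 2-10% events).

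**If only maintenance entrants are tabulated:** 1.02 to 1.11 (constant per sample, 10-40% dropout) or 1.07 to 1.16 (constant weekly hazard, 20% dropout).

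**Limits of the effect:** the ratio is 1.00 if all conversions, or all events, fall by Week 12.

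**After correction, same null models:** Induction-only table 0.95-1.02 (simulation noise); person-time rates with time-varying ADA status 1.00-1.01.

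**The case against.** **The population is not stated.** A reader might infer that Induction+Maintenance certainly pools 12-week patients with Week 104 patients. The documents do not settle this. SAP 6.14 puts all safety evaluations on the Safety Population, and 6.14.8.4 speaks of LY-treated patients; both point to inclusion. Against that, SAP 6.2 bases maintenance and extension analyses on the enrolled populations, the combined exposure formula in 6.14.1.1 has no term for patients who never entered maintenance, and Protocol Table AMAC.4 restricts the maintenance safety population to dosed LY responders. This objection stands: on the narrow reading the Induction+Maintenance effect is small. It does not rescue Induction+Extension, where extension non-responders leave at Extension Visit 6 while others continue.

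**Sampling does not stop at Week 12 for every non-responder.** It stops only for those who leave; Attachment 2 continues sampling in the extension. So 4 against 16 describes only Induction+Maintenance.

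**The larger ratios need conversions and events to continue after Week 12.** That is correct, and the documents give no Phase 2 rates. Continuation is plausible for one component: injection site reactions are in Table 8, but SC dosing starts only in maintenance (Protocol Table AMAC.1). Patients who left at Week 12 cannot have such a reaction.

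**The listing allows each tabulated event to be dated against ADA results.** That helps, and it would be too strong to say that a real relation becomes unreadable. But the listing covers only patients with ADA present or a Table 8 event, so it gives no person-time for the rest.

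**Stakes are low.** The table is descriptive, no test by ADA status is planned, and the primary endpoint is untouched. This also stands.

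**Conclusion.** The point holds in limited form. Crude percentages by ever-positive status over unequal follow-up can by themselves link ADA+ with events, and events before the first positive sample are credited to ADA+. The timing problem remains on every reading of the population, and the follow-up problem remains on every reading for Induction+Extension (roughly 1.05-1.6).

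For Induction+Maintenance the size depends on an unstated denominator: roughly 1.1-1.3 (hazards falling sharply) or 1.5-3.1 (hazards constant, with the high ADA rates noted) if Week 12 leavers are included, and about 1.02-1.16 if they are not. All of these figures rest on assumed rates.

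A reader might go further and say that time on study alone will produce an association. The documents do not support that: it requires both conversion and events to continue after Week 12. This is an inexpensive improvement to a descriptive table for an exploratory objective, not a threat to the trial's main conclusions.

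**What to change.** In SAP 6.14.8.4:

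1. State the population of each combined table, in particular whether LY patients who left at Week 12 are in Induction+Maintenance, and reconcile this with 6.2, 6.14 and 6.14.1.1.
2. Add the TEAE-by-TE-ADA table for the Induction Period alone, matching the neighbouring ADA, hypersensitivity and injection-site analyses.
3. In the combined tables, flag whether each event began before or after the first TE ADA+ sample.
4. Beside the crude percentages, give events per patient-year by time-varying ADA status: time before the first TE ADA+ sample counts as negative, time after it as positive. Take person-time from the exposure data, since the listing lacks ADA-negative, event-free patients.
5. State a rule for TE ADA Inconclusive patients, whose status is defined at patient level.
6. Note that maintenance samples are 8 weeks apart, so the conversion date is approximate and an event shortly after true conversion may be counted as ADA-negative.

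The cost is SAP wording, modest programming and a somewhat more complex table. No new data collection is needed.
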